2.6 Subgroup analyses

Purpose: To evaluate the heterogeneity of treatment effects by baseline characteristics of age, sex, previous antihypertensive medication, race, and baseline BP level.

Methods/Approach:

- To assess the heterogeneity of treatment effects by age, sex, previous antihypertensive medication and race, the two-way interactions of the main effects of treatments and these covariates will be assessed at the 0.2 significance level
- To assess the heterogeneity of treatment effects by baseline BP, we will divide the cohort into tertiles based on their initial BP level (median of three qualifying SBP from eligibility phase). We will repeat the above primary (Section 2.4) and secondary modeling (Section 2.5a) within each of the three initial BP strata to determine if there is heterogeneity of effect (e.g. do patients with the highest baseline BPs get the most benefit from the intervention components?).

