We will conduct additional exploratory analyses using the stratification factors (age, sex, and antihypertensive use) as covariates. As uncertainty exists on the distribution of enrolled participants within these strata (e.g. young men taking antihypertensive medication), we cannot estimate the preliminary statistical power for these exploratory aims. Thus, we will estimate the power based on the strata sizes prior to conducting the exploratory analyses. Interaction terms (e.g. age with behavioral interventions, sex with behavioral interventions, etc.) will be utilized to determine if specific groups respond well to specific intervention elements. Baseline BP may also play an important role. We will examine its impact by dividing the cohort into tertiles. We will repeat the above primary and exploratory modeling within each of the three initial BP strata to determine if there is heterogeneity of effect (e.g. do patients with the highest baseline BPs get the most benefit from the intervention components?). We will similarly assess the impact of the intervention components on the exploratory and process outcomes using linear, Poisson, logistic, or ordinal regression depending on the distributions. In addition, we will conduct longitudinal analyses that include all BP measurements over time (including those by text and at the in-person visits) to assess the temporal profiles of response in the intervention components.

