Sample Size: We plan to enroll approximately 960 patients into the eligibility phase. From this group, we estimate that 480 subjects will report qualifying BPs and will be randomized to one of the eight intervention arms. We anticipate 240 subjects will fully complete the 12 month, in person follow up visit. For 80% power to detect the smallest main expected effect of 0.35 based on the Collins method of a 3-factor experiment analyzed using a second order model (i.e. main effects and 2-way interactions), we require 196 subjects. Assuming 480 randomized subjects and allowing an additional 50% loss to follow up after the eligibility phase, we expect at

least 240 subjects, exceeding 80% power with an alpha level of 0.10 (inflated to reduce likelihood of dismissing active components with modest BP reducing effect) – we used the FactorialPowerPlan SAS macro to calculate power. For the secondary analyses, considering an alpha of 0.05 and a baseline proportion attending 2 or more primary care provider visits within one year of 40%, with a total sample size of 240 evenly distributed between the active appointment scheduling and passive appointment, we have 87% power to detect an increase to 60% attending 2 or more visits. The time to event analysis (considering an alpha of 0.05, power of 99%, and 240 subjects enrolled over 720 days, followed for 30 days) can detect a change from 20% of subjects in the non-facilitated group to 20.4% of subjects in the facilitated group.

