We will work to prevent missing data by the recruitment and retention strategies described elsewhere. The amount and patterns of missing data and its associations with other variables (in particular intervention category) will be explored so that an appropriate statistical method for analysis can be used. If the data is missing at random (missing outcomes can be predicted from other observed variables, especially recent self-reported blood pressures), which we believe to be the most likely, since we obtain text messaging-based BPs at least weekly, the repeated measurements within individuals will allow us to use multiple imputation to handle sporadic missing at random BP measurements. For multiple imputation, we will use R package mice to impute the data using multiple imputation by chained equations. Non-normal continuous missing variables will be transformed for normality and back-transformed for any calculations necessary (e.g., change in BP). The imputation model will include all variables in the analysis model, treatment interactions, as well as other covariates that predict the missing variable and whether the missing variable is missing. Thus, associations between baseline variables and missing variables will be assessed both for strength of association and functional form. We will use 100*fraction of incomplete cases number of imputations. Analyses will combine regression estimates using Rubin's rules. Model checking will be performed on each imputed dataset through residual analysis to identify any issues with the imputation model or analysis model. Problems occurring in a small number of imputed datasets suggest a problem with the imputation dataset and problems occurring consistently across all imputed datasets suggest a problem with the analysis model.

In the case of non-ignorable missing (missing not at random) data, sensitivity analyses will be performed using pattern mixture or selection models to evaluate the robustness of our conclusions to a range of sensible conditions (for both the primary and additional analyses of the primary endpoint).

Interpretation:

Results will be reported as parameter estimates, 95% confidence intervals, and 2-sided p-values. As the goal of this exploratory trial is to find interventions and combinations with activity, we will use an alpha level of 0.10 for all main effects. Plots of mean BP levels over time will be generated for the 3 main effects and each intervention group.

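### Heterogeneity by baseline BP is assessed only by separate models in each tertile, with no test of whether the tertile effects differ

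*SAP*

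**What the plan says.** SAP 2.6 names five baseline factors for heterogeneity of treatment effect. Four of them (race, sex, age and earlier use of antihypertensives) are covered by interaction tests: "the two-way interactions of the main effects of treatments and these covariates will be assessed at the 0.2 significance level". Baseline BP is handled differently: "we will divide the cohort into tertiles based on their initial BP level", using the median of the three qualifying SBP readings, and the models of SAP 2.4 and 2.5(a) are repeated "within each of the three initial BP strata to determine if there is heterogeneity of effect".

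Protocol 9.1 matches. It says "We will examine its impact by dividing the cohort into tertiles", and then "We will repeat the above primary and exploratory modeling within each of the three initial BP strata". Both documents give the same example question, namely whether the patients with the highest baseline BPs gain most.

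Neither document gives a treatment-by-baseline-BP term, a contrast between tertiles, or a rule for calling the tertile results different. For main effects, SAP 2.4 says "we will use an alpha level of 0.10 for all main effects" and reports parameter estimates with "95% confidence intervals, and 2-sided p-values". SAP 2.5(c) makes no multiplicity adjustment.

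**The concern.** Whether patients with the highest baseline BP gain more is a question about the difference between strata. Three separate fits give three estimates and three p-values, and none of these measures that difference. With about a third of the completers in each tertile, a component that works equally well throughout can easily reach the 0.10 bar in one tertile and miss it in another. A report might then describe a differential response that the data do not show. The section already contains a suitable method and applies it to the other four factors, so baseline BP alone is left without a test. Because no rule is stated, the conclusion would rest on judgement after the results are seen.

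**Working it through.** **Inputs.**
- 240 expected completers (SAP section 1, Sample Size; still the target in Protocol 9.3), so 240/3 = 80 per tertile.
- Two-sided alpha 0.10 for main effects (SAP 2.4).
- Equal allocation to the two levels of each component (the 2x2x2 design).
- Planning effect: "For 80% power to detect the smallest main expected effect of 0.35" (SAP section 1). Protocol 9.3 equates it with 1 mm Hg on an SD of 2.8 mm Hg, and 1/2.8 = 0.357.

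**The plan's own figure.** The documents require 196 participants. The normal approximation is N = 4(1.645 + 0.842)²/d². This gives 194 at d = 0.357 and 202 at d = 0.35. A noncentral-t calculation with the seven parameters of a second-order model gives exactly 196 at d = 0.357. The stated figure therefore reproduces, and the inputs are read as the plan intends.

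**Power within one tertile.** With n per tertile,

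p = Φ(d√n/2 − 1.645) + Φ(−d√n/2 − 1.645).

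At d = 0.35 and n = 80, d√n/2 = 1.565 and p = 0.469 (noncentral t: 0.463).

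**Chance of discordant tertiles when the true effect is the same in all three.** The SAP has no rule, so assume that tertiles are compared by whether each reaches p < 0.10. The results disagree unless all three or none are significant:

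P(discordant) = 1 − p³ − (1 − p)³.

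| Common effect | n per tertile | p | P(discordant), one component |
|---|---|---|---|
| 0 | 80 | 0.100 | 1 − 0.001 − 0.729 = 27% |
| 0.175 SD | 80 | 0.202 | 1 − 0.008 − 0.508 = 48% |
| 0.35 SD | 80 | 0.469 | 1 − 0.103 − 0.150 = 75% |
| 0.35 SD, full information on 480 | 160 | 0.715 | 1 − 0.366 − 0.023 = 61% |
| 0.35 SD, full information on 720 | 240 | 0.857 | 1 − 0.629 − 0.003 = 37% |

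The 720 is 480 × 1.5, the increased maximum in Protocol 9.3. The formula peaks at exactly 75% when p = 0.5, so the planning effect sits practically at its maximum. The per-component figure exceeds one half only for common effects of about 0.19 to 0.55 SD. With a 0.05 cut-off, the 75% becomes 68% (p = 0.347).

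Treating the three components as independent, the chance that at least one is discordant is 1 − 0.73³ = 61% at zero effect and 1 − (1 − 0.747)³ = 98% at 0.35 SD.

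**Simulation check.** The SAP 2.4 model was fitted in each tertile in 6,000 simulated trials per scenario, with assumed covariate prevalences and unit residual SD. Per-component discordance was 26–27% at zero effect, 47–48% at 0.175 SD and 73–74% at 0.35 SD.

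**An interaction test instead.** At the 0.2 level, a valid test gives false heterogeneity in 20% of trials per component, and in 1 − 0.8³ = 48.8% for at least one of three. A component-by-tertile F test in the same simulated trials gave 19–21% and 48–49% at all three effect sizes. The continuous interaction proposed below was not itself simulated; its 20% follows from the level of the test.

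**The case against.** The strongest reply is that the comparison rule is assumed. Neither document says that tertiles will be judged as significant or not. Repeating the SAP 2.4 analysis yields an estimate and a 95% interval in each tertile, and a careful reader could compare those. This stands: every percentage for the tertile method depends on the assumed rule. It does not supply the missing comparison, though, and the lack of a rule is part of the problem.

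The size is also open to challenge. SAP 2.4 is an intention-to-treat analysis of all randomized participants, with multiple imputation if data are missing at random, so 80 per tertile is the least favourable case. The 61% and 37% figures are the opposite limits, since imputation does not restore full information. Not every discordant pattern answers the example question either: one that falsely points to the upper tertiles (top only, or top two, significant) has probability p(1 − p) = 0.463 × 0.537 = 25%.

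A reader might infer that the tertile method usually finds a difference where none exists. That is too strong per component: the figure is 27% at zero effect and passes one half only in the middle range of effects. A reader might also infer that the analysis would misdirect the choice of population for the next trial. The documents do not support that. The go-forward rule in Protocol 9.1 and SAP section 1 selects components and their combinations, and nothing in either document lets tertile results select a population.

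**Conclusion.** The gap is real and limited. As written, the plan cannot answer its own question about baseline BP, because nothing in it compares the tertiles. If tertiles are compared by significance at 0.10 with 240 completers, a common effect produces discordant results per component in about 27% to 75% of trials over the range from zero to the planning effect. The 75% would fall to between 61% and 37% only if imputation recovered full information on 480 to 720 participants. The rate varies with the unknown size of the common effect, so it cannot be allowed for when the results are read.

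The consequence is confined to the reading of heterogeneity in a trial that calls itself exploratory. The primary result and the component selection rule are unaffected. The change is still worth making because it costs little and uses a method already in the same section.

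**What to change.** In SAP 2.6, specify a separate subgroup model: the SAP 2.4 model plus continuous baseline SBP (the median already defined) and its interaction with each of the three components. Leave the primary model in SAP 2.4 unchanged. Base any statement about heterogeneity by baseline BP on the interaction terms, at the 0.2 level used for the other four factors. Keep the tertile estimates with intervals as a descriptive display, and say that significance in one tertile but not in another will not be read as heterogeneity. Align Protocol 9.1.

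The cost is wording and one additional model, with no new data, visits or participants. Two drawbacks should be stated in the SAP. At 0.2 the false-positive rate is 20% per component and about 49% for at least one of three, so at zero effect the improvement on 27% and 61% is modest; the main gain is an error rate that is known and does not depend on the size of the common effect. A linear interaction can also miss a threshold pattern, which is a reason to keep the tertile display.

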2.7 Exploratory analyses

Endpoints:

BP

- Proportion of subjects achieving BP control (control = 6/12 month BPs are achieving target recommendations as defined by JNC8)
 - JNC-8 targets for SBP/DBP
 - 2017 AHA guidelines targets for SBP/DBP
- Change in DBP and mean arterial pressure
- Change in 6 month SBP

Process

- Number of interactions (such as calls/texts) to schedule subject initial primary care visit
- Number of interactions to schedule all other primary care visits
- Proportion of BPs texted to the study team
- Proportion enrolled but not randomized

PCP

- Establishment of a primary care providers among those without
- Self-reported number and proportion of provider visits attended
- Proportion of transportation vouchers used

Utilization

- Frequency of Hurley ED and other healthcare visits
- Self-reported follow up of emergency department visits
- Self-reported follow up of provider or clinic visits

Medications

- Changes/escalation in antihypertensive regimen through patient self-report
- Medication Adherence (Hill-Bone Scale, and modified Hill-Bone instrument asking, “How often do you forget to take your HBP medicine?”)

Other

- Social Cognitive Theory (SCT) measures
 - Modified one-question self-efficacy measure, “I am confident that I can take my blood pressure and text it to the Reach Out Team”)
 - Questions querying self-efficacy, motivation, social support and expertise.
 - I am confident that I can control my blood pressure
 - It is worthwhile for me to control my blood pressure
 - My friends and family care if I control my blood pressure
 - I know the right steps to take to control my blood pressure

Methods/Approach:

We will similarly assess the impact of the intervention components on the exploratory and process outcomes using linear, Poisson, logistic, or ordinal regression depending on the distributions. The main effects will be

tested at the $p=0.1$ level adjusting for age, sex, previous antihypertensive use, and race. Treatment interactions will be explored at the 0.2 level.

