5.3.4 Eligibility phase

Following consent, because some participants will have isolated hypertension in the ED, participants will undergo a 3-week eligibility phase (beginning after informed consent, and participant has received blood pressure cuff) to determine if they have persistently elevated BP. All participants enrolled in the study will be given an automated BP cuff, American Heart Association or American College of Cardiology information about high blood pressure (Appendix B), and receive a text message one day in a week asking to text in their own BP. If a participant has not responded by the end of week 2 of the eligibility phase, a study team member may contact up to 2 times to assure it is not a technical issue. This is based on feedback from our previous studies, where participant's primary reported reason for unresponsiveness was unaddressed technical complications.

If participants have 1) persistent high blood pressure (any self-reported BP (SBP) \geq 140 or a BP (DBP) \geq 90), and 2) responded to texts at least once, they will be randomized into the trial. If participants do not meet both criteria, they will receive no further communication from the study team following the eligibility phase. These participants may be texted a final text message thanking them for participation.

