26.	SCT	Reinforcement	PHYSICAL ACTIVITY	Stress can make exercise seem overwhelming and hard. Keep at your health goals and try to take it one day at a time! ☺
27.	SCT	Knowledge	PHYSICAL ACTIVITY	Try using commercial breaks while watching TV as a time to get up and get moving! Try doing some, lunges, jumping jacks or jogging in place!
28.	SCT	Knowledge	PHYSICAL ACTIVITY	Don't forget that being active can be more than going for a run or hitting the gym! Try gardening, biking, or even a walk to get yourself up and moving!
1.	SCT	MEDICATION ADHER- ANCE		It is very important to regularly take your BP medication, get help by asking people close to you to remind you. Often the more support you have the better!
2.	SCT	MEDICATION ADHER- ANCE		Don't forget to regularly take your BP meds, and do not stop any medications without talking to your health care provider first. Consistency is very important!
3.	SCT	MEDICATION ADHER- ANCE		Remember to take your BP meds every day. If you don't feel like your meds are making a difference, or you're having side-effects, your Dr can help, go see them!
4.	SCT	MEDICATION ADHER- ANCE		Often cost of BP meds are a challenge, but there are discount, BPmeds at many stores, such as Kmart, Meijer, Walmart, CVS, and Walgreens.
5.	SCT	MEDICATION ADHER- ANCE		Many stores like Kmart, Meijer, Walmart, CVS, and Walgreens provide discounted BP meds. Save money by checking to see if your BP meds are cheaper there.

6.	SCT	MEDICATION ADHER- ANCE	If you find yourself having trouble remembering to take your BP meds, use a beeping alarm or watch to remind you when a dose is due, and to keep consistency!
1.	SCT	Med Encouragement	It's not always easy to decide when it's time to start taking BP meds, but most people need meds in addition to exercise and diet to lower their high BP.
2.	SCT	Med Encouragement	Often cost of BP meds are a challenge, but there are discount, generic meds at many stores, such as Kmart, Meijer, Walmart, CVS, and Walgreens.
3.	SCT	Med Encouragement	Think about how important it is to you to lower your BP, then start taking small steps towards change. One important step may be beginning BP medication.
4.	SCT	Med Encouragement	If your healthy habits aren't enough to bring your BP below 140/90, you may need to take BP medication, and this is something a Dr can help you decide.

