2.4. Primary analysis/results

Purpose: Primary results for the intention to treat (ITT) analysis.

Methods/Approach:

Intention to Treat Dataset: all subjects randomized into study and all data observed from each subject regardless of compliance and adherence with the assigned intervention or follow-up.

Primary outcome: Change in systolic BP from baseline (median of three qualifying SBP from eligibility phase) to 12 months. Baseline minus 12 months.

Primary analysis: The primary analysis will fit a linear regression model with the outcome of SBP change and main effect-coded binary predictors of healthy behavior texts (yes vs. no), prompted BP self-monitoring frequency (high vs. low), and primary care provider visit scheduling and transportation (active vs. passive) and the stratification variables. Initial analyses will focus on the main effects. The outcome will be transformed (e.g., log) if necessary.

$$(BL\ BP - 12\ mo\ BP) = \beta_0 + \beta_1\ HBtexts + \beta_2\ HighBPmonitor + \beta_3\ PCPfacilitated + \beta_4\ female + \beta_5\ Age > 65 + \beta_6\ AHT + \beta_7\ Black$$

Where HBtexts= 1 for daily healthy behavior texts and 0 for none; HighBPmonitor=1 if daily BP monitoring and 0 for weekly; PCPfacilitated=1 for provider scheduling and transportation facilitated and 0 for not facilitated; female = 1 for self-reported female, 0 for male; Age>65=1 for Age \geq 65, 0 for 18-64; and AHT=1 for antihypertensives in the past 6 months, 0 for not; Black=1 for Black, 0 for Other

Missing data:

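### The BP-control models in SAP 2.7 omit baseline BP, and the raw proportion at target cannot be read as control gained

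*SAP*

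**What the plan says.** SAP 2.7 gives the endpoint as "Proportion of subjects achieving BP control (control = 6/12 month BPs are achieving target recommendations as defined by JNC8" and lists both JNC-8 and 2017 AHA targets, without numbers. Main effects are tested at 0.10, adjusted for age, sex, previous antihypertensive use and race. Baseline BP is not in that list, and nobody has to be above target at baseline to be counted.

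Protocol 5.3.4 sets the entry rule. Participants "receive a text message one day in a week asking to text in their own BP" for three weeks, so about three readings at most. The BP criterion is "any self-reported BP (SBP) \geq 140 or a BP (DBP) \geq 90", and those who also "responded to texts at least once, they will be randomized into the trial". One reading can therefore be enough.

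SAP 2.4 defines the primary outcome as "Change in systolic BP from baseline (median of three qualifying SBP from eligibility phase) to 12 months"; Protocol 1.1 uses the same baseline.

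**The concern.** Under an entry rule of any one elevated reading, some participants will have a baseline median below the threshold that admitted them, and others will fall below it later through ordinary variation between readings. An endpoint worded as achieving control counts both groups as successes.

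Two things are at stake. Baseline level predicts who is at target later, so leaving it out of the logistic model gives up precision in the component contrasts. And a reader may take the raw proportion as control gained. That matters most if it is set beside the retrospective group in Protocol section 3: those patients were not selected on a home reading, so randomisation does not balance the effect of the entry rule in that comparison.

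**Working it through.** **No plan figure to reproduce.** The documents give no expected control rate and no power for this endpoint. The only SD, 2.8 mm Hg in Protocol 9.3, belongs to the standardised effect and does not describe the spread of home readings.

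**Inputs from the documents.** Any one reading of at least 140 or 90 qualifies; up to about three readings; baseline is their median; 240 completers; alpha 0.10. The expected qualifying share is 480/960 = 50%, and the pilot in Protocol 2.2.2 had 55/104 = 53%. The 50% also counts people who never texted, so the share among responders should be higher.

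**Assumed inputs.** Targets of 140/90 or 130/80; mean home SBP 125-155; SBP SD 12-18 between persons and 8-12 within; DBP SDs 0.6 times these; SBP-DBP correlation 0.6; no treatment effect and no time trend.

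**Step 1: one case.** Readings of 138/86, 142/84 and 136/88 qualify through the 142. The medians are 138 (of 136, 138, 142) and 86 (of 84, 86, 88). This person is below 140/90 at baseline and counts as controlled if nothing changes.

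**Step 2: one entry reading, SBP only, by hand.** Take mean 140, between-person SD 15 and within-person SD 10. The correlation between two readings is 225/(225 + 100) = 0.692. With the threshold at the mean, P(both at or above) = 1/4 + arcsin(0.692)/(2π) = 0.25 + 0.765/6.283 = 0.372. So P(follow-up below 140, given entry) = 1 - 0.372/0.5 = 26%. Nobody here was at target at baseline; all of it is regression to the mean.

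**Step 3: three entry readings, simulated, target 140/90.** The last four columns use SBP SD 15 between and 10 within.

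| Responders qualifying | At target at follow-up, all SDs | At target at follow-up | Already at target on baseline median | Of those at target at follow-up, already there at baseline | At target at follow-up, of those above at baseline |
|---|---|---|---|---|---|
| 50% | 34-53% | 46% | 42% | 61% | 31% |
| 70% | 24-39% | 34% | 30% | 53% | 23% |
| 90% | 11-22% | 18% | 14% | 41% | 12% |

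Check of the 50% row: 0.46 × 0.61 = 0.28 are at target both times, and (0.46 - 0.28)/(1 - 0.42) = 0.31. Over the full grid the follow-up rate is 9-53% and the share already at target 27-65%. At 130/80 the follow-up rate is about 1-22%.

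**Step 4: power.** Simulated trials of 240 completers, three entry readings, between-person SD 15/10 (SBP/DBP), visit-to-visit SD 10/7, target 140/90, two-sided alpha 0.10, 5 mm Hg component effect:

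| Mean home BP | No baseline BP | With baseline SBP and DBP | Gain |
|---|---|---|---|
| 132/81 | 70% | 75% | 5 |
| 140/85 | 63% | 71% | 8 |
| 148/90 | 55% | 66% | 11 |

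Two further runs at 132/81 gave 66% to 74% and 68% to 77%. With 1,500 trials the simulation error is about √(0.7 × 0.3/1500) = 1.2 points. At 3 mm Hg the gain was 5 to 8 points (36% to 41%, 34% to 42%). Type I error was 9-10%. Restricting the test to those above target at baseline gave 52% at 5 mm Hg, against 66% unadjusted and 74% adjusted with everyone kept.

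**The case against.** The strongest reply is that nothing important depends on this. All arms share the entry rule, so the component contrast is unbiased, and that contrast is what SAP 2.7 sets out to assess. The endpoint is one of many exploratory ones, with no power claim and no decision rule; components are selected on SBP change. SAP 2.3 already tabulates baseline BP by group. All of this stands, and it sets the priority. It does not supply the missing covariate: the baseline-tertile analyses in SAP 2.6 repeat the modelling of 2.4 and 2.5(a), not of 2.7.

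The rates also cannot be derived from the documents. A reader might infer that about a third of participants would show control with no effect. That is only a mid-range value under one set of assumptions. No endpoint target is given in numbers: 140/90 appears as the entry threshold and in a sample message ("enough to bring your BP below 140/90"), while Protocol 6.1.3 uses systolic below 130 for appointment frequency.

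A reader might also infer that some of those counted were never above target. At 140/90 the documents rule this out: Protocol 5.1 requires an ED reading of at least 160 or 100, and 5.3.4 an elevated home reading. At most, a baseline median lies below target.

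Finally, being at target at baseline is impossible at 140/90 when only one reading was sent. It is also impossible for SBP if three qualifying SBPs means that all three were at least 140. That reading conflicts with the any-reading rule in 5.3.4.

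**Conclusion.** The point holds as one of precision and interpretation, not of bias. Leaving out baseline SBP and DBP costs roughly 5 to 10 points of power at 5 mm Hg with 240 completers. With no effect, about 10-50% would be at an assumed 140/90 target at follow-up, and about 1-22% at 130/80. With three entry readings, roughly 40-60% of those at 140/90 were in most settings already there on the baseline median. Every figure depends on assumed BP means, SDs and targets.

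It would be tempting to conclude that counting only participants above target at baseline solves the problem. It does not: the no-effect rate is still 12-31% in the table (about 7-37% over the settings checked), and using that restriction for the test lowers power. The primary analysis is not affected by this point.

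**What to change.** In SAP 2.7:

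- Keep all participants in the BP-control models and add baseline SBP and DBP, as eligibility-phase medians. The SAP defines the median only for SBP, so the DBP counterpart needs a line.
- Beside each follow-up proportion, report the share already at that target at baseline, by component level.
- Describe the endpoint as being at target rather than achieving control, separately at 6 and 12 months, with the intended numeric targets written out.

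Reconcile the any-reading entry rule in Protocol 5.3.4 with the median of three qualifying SBPs in Protocol 1.1 and SAP 2.4, and say what baseline is when fewer than three readings were sent.

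The cost is SAP wording and one extra table, with no new data. The raw proportion will read less favourably. Priority is low because the endpoint is exploratory.
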